9.1 Study endpoints

9.1.1 Primary endpoint(s)

Primary efficacy outcome will be a composite score based on EDSS (our EDSS assessments will be based only on pyramidal and brainstem FSS, and performed by a blinded examiner), T25FW, and 9HPT (EDSS-Plus) [6]. Improvement will be defined by at least one of the following three measures: ≥ 0.5 improvement in EDSS (if EDSS at entry is ≥ 6.0) or ≥ 1.0 improvement in EDSS (if EDSS at entry is ≤ 5.5), $\geq 20\%$ improvement in T25FW, or $\geq 20\%$ improvement in 9HPT in either dominant or non-dominant upper limb. Scores will be compared within patients between the baseline and various post-treatment visits. Scores will also be compared between different treatment groups at various post-treatment visits. Assessments will be made at Baseline (within 4 months of first treatment/placebo), Month 6 (just prior to 4th

treatment/placebo), Month 13 (3 months post 6th treatment/placebo), Month 20 (just prior to 10th treatment/placebo), and Month 27 (3 months post 12th treatment/placebo). Long-term follow-up assessment will be conducted at Month 36. The primary outcome will be the comparison of the composite scores at Month 13 (3 months after the 6th treatment/placebo) compared to baseline.

9.1.2 Secondary endpoints

- EDSS (Improvement defined by ≥ 0.5 improvement in EDSS if EDSS at entry is ≥ 6.0 , or ≥ 1.0 improvement in EDSS if EDSS at entry is ≤ 5.5)
- T25FW ($\geq 20\%$ improvement)
- 9HPT ($\geq 20\%$ improvement)
- MSFC
- 12-item MS Walking Scale
- Urodynamic Studies
- Progression on MRI (measured by percent change from baseline in total volume of T2 Lesions and percent change from baseline in total brain volume at month 13, month 27, and month 36)
- Time to Progression (measured at month 13, month 27, and month 36)
- Six Minute Walk Test

9.2 Sample size determination

Power analysis was conducted by [name], Professor of Healthcare Policy & Research and Professor of Epidemiology in Medicine at Weill Cornell Medicine, who will provide statistical consultations throughout the study. Power analysis was based on 20 participants in each group of the Phase II study. Group sample size of 20 in the treatment group and 20 in the placebo group achieve more than 80% power to detect a difference between the group proportions of 35%, using a two-sided Z-test with pooled variance and using a significance level of 0.05. This calculation assumes that 40% of patients in the treatment group and 5% of patients in the placebo group achieve at least one of the EDSS-Plus components. The prevalence of patients with improved outcome is informed by the results of our Phase I trial, in which 40% of patients experienced a decrease of 0.5 or more on EDSS. A total of 50 patients (25 patients in each group) will initially be enrolled to account for an expected attrition rate of 20%.

9.3 Effectiveness analysis

All statistical analysis will be performed by [name] and her team. Descriptive statistics will be calculated for patients at baseline for the entire cohort

as well as by treatment status. Treatment and placebo group patients will be compared on continuous and discrete baseline characteristics to assess randomization. The EDSS-Plus scale [6] will be used as our primary endpoint with improvement on one or more of the 3 components (EDSS, T25FW and 9HPT). Improvement is defined as ≥ 1 point decrease from baseline EDSS if EDSS at entry is ≤ 5.5 , and a ≥ 0.5 point decrease from baseline EDSS if EDSS at entry is ≥ 6.0 , $\geq 20\%$ positive change in T25FW, and/or $\geq 20\%$ positive change in 9HPT confirmed. The primary endpoint of improvement on one or more of the 3 EDSS-Plus categories between treatment and placebo groups will be assessed bi-varately using the chi-square or Fisher's exact test, as appropriate, at year 1, 2, and 3 of the study. The three components of the EDSS-Plus composite score will also be assessed individually at all time points. A longitudinal linear mixed-effect model will be used to assess longitudinal change (percentage change in mean time) from baseline to 3 years for T25FW and 9HPT, with random intercepts for patients and taking into account treatment status (treatment vs placebo), progression status (SPMS vs PPMS) and time-progression status interaction. Secondary endpoints including 12-item walking scale and urodynamic studies (binary, $\geq 20\%$ improvement in bladder capacity vs $< 20\%$) will also be analyzed. Linear regression models for continuous outcomes and logistic regression models for discrete outcomes will be used to assess the independent effect of treatment status on secondary outcomes, controlling for co-variates. All analyses will be performed in SAS Version 9.4 (SAS Institute Inc., Cary, NC).

Any deviations from the previously described statistical plan will be described and justified in a protocol amendment and/or in the final report submitted to the IND application.

9.4 Safety analysis

Safety analysis will be performed on the analysis population. Safety will be assessed through summaries of serious adverse events, minor adverse events including headache and fever, and neurological disease worsening (neurological assessments and MRI). All adverse events occurring on or after the first lumbar puncture will be coded and summarized by NCI CTCAE v4.0 criteria.

9.5 Data and Safety Monitoring Committee

A Data Safety Monitoring Board (DSMB) will review safety data and make recommendations to the investigators about any existing or potential problems. The Data Safety Monitoring Board will be comprised of four members. The first three include: [name], PhD, [name], and [name], PhD (Chairman) with expertise in medicine, neurology, basic research, stem-cell research, and ethical and legal matters. The fourth member, [name] is a biostatistician independent of our trial, who has valuable expertise to add given his long history of serving on DSMB boards. The board will include members with

no conflict of interest and are blinded to patient identity. DSMB procedures will be conducted according to the DSMB charter. The DSMB will meet by teleconference at the beginning of the study and yearly thereafter. All serious adverse events will be reported to the DSMB within 24-48 hours. An ad hoc meeting of the DSMB may be called at any time by the DSMB Chair or the investigator if participant safety issues arise. If a significant safety concern arises during the study, or upon withdrawal of a study participant from the study, the DSMB Chair may convene a meeting to review safety and any other aspect of the study. At meetings, they will review safety data from all subjects enrolled. The DSMB has the discretion to remove an individual from the study or terminate the study if need be. The Data Safety Monitoring Board will address clinical protocol violations if they arise. Violations in clinical protocol will be monitored by the DSMB. The Board will speak with the clinical researchers about protocol violations and will have the authority to investigate if they feel there is a violation occurring. Violations in the laboratory protocol will also be monitored by the Data Safety Monitoring Board. The Board will speak to the head of the laboratory research and will have the authority to investigate if it is suspected that a violation has occurred.

10. Quality Control and Quality Assurance:

Monitoring of the clinical study for protocol and GCP compliance will be conducted periodically by the DSMB

The Sponsor-Investigator will permit direct access of the DSMB and appropriate regulatory authorities to the study data and to the corresponding source data and documents to verify the accuracy of this data.

Study will be monitored to insure:

- Accuracy and Completeness
- Compliance with the FDA, HIPAA, and other appropriate regulations
- Compliance with ICH GCP and related standards
- Compliance with the protocol requirements
- Compliance with IRB requirements
- Compliance with tissue processing and related standards and practices
- Accuracy of Data Management practices

11. Data Handling and Record-Keeping:

11.1 Data recording/Electronic Case Report Forms

An electronic Case Report Form (eCRF) will be completed for each subject enrolled into the clinical study. The Sponsor-Investigator will review, approve and sign/date each completed CRF; the Sponsor-Investigator's signature serving as attestation of the Sponsor-Investigator's responsibility for ensuring that all clinical and laboratory data entered on the CRF are complete, accurate and authentic.

Source Data are the clinical findings and observations, laboratory and test data, and other information contained in *Source Documents*. *Source Documents* are the original records (and certified copies of original records); including, but not limited to, hospital medical records, physician or office charts, physician or nursing notes, subject diaries or evaluation checklists, pharmacy dispensing records, recorded data from automated instruments, x-rays, etc. When applicable, information recorded on the eCRF shall match the *Source Data* recorded on the *Source Documents*.

Each study subject will have an electronic file electronic Case Report Form (eCRF). The eCRF will contain results from all screens used to assess patients. These include results from:

- ICF
- Physical examinations
- Vital signs
- Neurological examinations
- Each EDSS
- Each MSFC
- Each 6 Minute Walk Test
- Each 12 Item MS Walking Scale
- Each Headache Pain Scale
- Each Infectious Disease Questionnaire
- Bladder Survey
- Lab and Urine Results
- MRI Reports
- Pregnancy test for female patients of child-bearing age
- Urodynamics testing reports
- Bone Marrow Aspiration Record
- Lumbar Puncture Record

11.2 Record maintenance and retention

The Sponsor-Investigator will maintain records in accordance with Good Clinical Practice guidelines; to include:

- FDA correspondence related to the IND and clinical protocol, including copies of submitted Safety Reports and Annual Reports
- IRB correspondence (including approval notifications) related to the clinical protocol; including copies of adverse event reports and annual or interim reports
- Current and past versions of the IRB-approved clinical protocol and corresponding IRB-approved consent form(s) and, if applicable, subject recruitment advertisements
- Copies of initial and continuing IRB approval notifications
- Signed FDA Form 1572 Statements of Investigator
- Financial disclosure information (i.e., for the Sponsor-Investigator; also for all study site sub-investigators who will be involved in the administration of the study drugs and/or the evaluation of research subjects [i.e., who will contribute significantly to the study data])
- Curriculum vitae (i.e., for the Sponsor-Investigator and investigators responsible for the conduct of the clinical research study)
- Certificates of required training; e.g., human subject protections, Good Clinical Practice, etc. (i.e., for the Sponsor-Investigator and investigators responsible for the conduct of the clinical research study; also for all study site sub-investigators who will be involved in the administration of the study drugs and/or the evaluation of research subjects [i.e., who will contribute significantly to the study data])
- Listing of printed names/signatures. (i.e., for the Sponsor-Investigator and investigators responsible for the conduct of the clinical research study; also for all study site sub-investigators who will be involved in the administration of the study drugs and/or the evaluation of research subjects [i.e., who will contribute significantly to the study data])
- Normal value(s)/range(s) for medical/laboratory/technical procedures or tests included in the clinical protocol
- Laboratory certification information for study site
- Instructions for on-site preparation and handling of the investigational drug(s), study treatment(s), and other study-related materials (i.e., if not addressed in the clinical protocol)
- Responsibility delegation log
- Signed informed consent forms
- Completed electronic Case Report Forms; signed and dated by Sponsor-Investigator
- Source Documents or certified copies of Source Documents
- DSMB reports for study site
- Copies of Sponsor-Investigator correspondence (including notifications of safety information) to sub-investigators
- Subject screening and enrollment logs
- Subject identification code list
- Investigational drug accountability records
- Final clinical study report
- Decoding procedures
- Master randomization list

- Retained biological specimen log
- Interim data analysis report(s)
- Copies of Sponsor-Investigator correspondence (including notifications of safety information) to Investigators responsible for the conduct of the clinical research study

The Sponsor-Investigator will retain the specified records and reports for up to 2 years after the marketing application is approved for the investigational drug; or, if a marketing application is not submitted or approved for the investigational drug, until 2 years after investigations under the IND have been discontinued and the FDA so notified.

12. Ethics:

12.1 Institutional Review Board (IRB) approval

The Sponsor-Investigator will obtain, from Western IRB (WIRB), prospective approval of the clinical protocol and corresponding informed consent form(s); modifications to the clinical protocol and corresponding informed consent forms, and advertisements (i.e., directed at potential research subjects) for study recruitment.

The only circumstance in which a deviation from the current IRB-approved clinical protocol/consent form(s) may be initiated in the absence of prospective IRB approval is to eliminate an apparent immediate hazard to the research subject(s). In such circumstances, the Sponsor-Investigator will promptly notify WIRB of the deviation.

The Western IRB operates in compliance with FDA regulations at [21 CFR Parts 50](#) and [21 CFR 56](#), and in conformance with applicable International Conference on Harmonization (ICH) Guidelines on Good Clinical Practice (CGP).

In the event that WIRB requires, as a condition of approval, substantial changes to a clinical protocol submitted under an FDA-accepted IND application, or in the event of the Sponsor-Investigator's decision to modify the previously accepted clinical protocol:

- The Sponsor-Investigator will submit (i.e., in advance of implementing the change) a Protocol Amendment to the IND describing any change to the Phase protocol that significantly affects the safety of subjects, the scope of the investigation, or the scientific quality of the study.

12.2 Ethical and scientific conduct of the clinical research study

The clinical research study will be conducted in accordance with the current IRB-approved clinical protocol; ICH GCP Guidelines adopted by the FDA; and relevant policies, requirements, and regulations of the Western IRB, and applicable state and federal agencies.

12.3 Subject informed consent

The Sponsor-Investigator will make certain that an appropriate informed consent process is in place to ensure that potential research subjects are fully informed about the nature and objectives of the clinical study, the potential risks and benefits of study participation, and their rights as research subjects. The Sponsor-Investigator, or a sub-investigator(s) designated by the Sponsor-Investigator, will obtain the written, signed informed consent of each subject prior to performing any study-specific procedures on the subject. The date and time that the subject signs the informed consent form and a narrative of the issues discussed during the informed consent process will be documented in the subject's case history. The Sponsor-Investigator will retain the original copy of the signed informed consent form, and a copy will be provided to the subject, or to the subject's authorized representative.

The Sponsor-Investigator will make certain that appropriate processes and procedures are in place to ensure that ongoing questions and concerns of enrolled subjects are adequately addressed and that the subjects are informed of any new information that may affect their decision to continue participation in the clinical study. In the event of substantial changes to the clinical study or the risk-to-benefit ratio of study participation, the Sponsor-Investigator will obtain the informed consent of enrolled subjects for continued participation in the clinical study

13. Study Discontinuation Criteria:

13.1 Discontinuation of individual research subjects (refer also to sections 5.1.1 and 8.4)

If any of the following events occur during treatment, patients will be discontinued from the study:

- Acute worsening of MS symptoms
- Any neurological deficit that is unexplained by another condition and is non-reversible within 24 hours of its development
- Any sign of debilitating infection or central nervous system infection
- Any changes in cognitive function
- Any unexpected adverse medical event that is unexplained by another medical condition
- Any time the Data Safety Monitoring Board feels a patient should be withdrawn from the study

- Patient's desire to withdraw
- Patient's inability to comply properly with study requirements (inability to make scheduled appointments, etc.)
- Patient meets an exclusion criterion
- Patient becomes incarcerated
- Pregnancy

Should a patient meet any of the above criteria for early termination, he or she will be discontinued from the trial and will not be replaced. Subjects that are discontinued from the study will continue to undergo the follow-up visits relative to their last treatment. They will also undergo follow-up long term safety visits as described. All data gathered at these appointments will be included in the CRF and data set. Should a study subject terminate the study due to pregnancy, no MRI will be performed during the course of the pregnancy.

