 - EDSS-Only if not performed at screening
 - MSFC
 - 6 Minute Walk Test
 - 12 Item MS Walking Scale
 - Bladder Survey
 - Urinalysis and Culture to screen for UTI
- The following exams will be scheduled to occur within one month prior to the first treatment
 - MRI (brain, C and T spine) ± Gadolinium enhancement
 - Urodynamic testing of bladder compliance (ability of bladder to fill without accompanying rise in bladder pressure)

Treatment Phase visits, year 1 (Month 0, 2, 4, 6, 8, and 10):

- Treatment/placebo visits will be conducted at the Tisch MSRCNY every 2 months (\pm 1 week)
- Details regarding treatment/placebo procedures detailed in section 5.2.2 above
- Treatment visits will be conducted by the treating neurologist, [name]
- Duration of treatment visits will last approximately 5 hours
- Study subjects will be instructed to stay in bed and limit any physical activity for the 24 hours following each procedure.
- CSF for biomarker analysis discussed in 5.2.2
- Blood draw for serum and plasma biomarker analysis
- Vital Signs
- EDSS and MSFC (Month 6 Only) Follow-up by phone will occur 48 hours, 1 week and 1 month after each treatment visit. The purpose of the follow-up phone call is safety assessment and to document any adverse events. Calls will be made either by the clinical trial manager, the clinical research assistants, or the adverse event physician. Assessment will include the following:
- Headache pain scale

Outcome assessments I (Month 13)

- The purpose of outcome assessment I visit is to evaluate effects of the treatment compared to the baseline visit, as well as to serve as a baseline visit for the crossover treatment phase.
- The following exams will be conducted 3 months following the 6th treatment phase visit (\pm 1 week)
 - Vital signs
 - Physical exam
 - Neurological exam
 - Headache pain scale
 - EDSS
 - MSFC
 - 6 Minute Walk Test
 - 12 Item MS Walking Scale
 - Bladder Survey
 - Urinalysis and Culture to screen for UTI
- The following exams will be scheduled to occur 3 months following the 6th treatment visit (\pm 1 week)
 - MRI (brain, C and T spine) \pm Gadolinium enhancement
 - Urodynamic testing of bladder compliance (ability of bladder to fill without accompanying rise in bladder pressure)

Treatment Phase visits, year 2 (Month 14, 16, 18, 20, 22, and 24):

- Crossover treatment/placebo visits will be conducted at the Tisch MSRCNY every 2 months (\pm 1 week)

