6.3 Follow-up procedures

- Treatment phase follow-up: Follow-up by phone will occur 48 hours, 1 week and 1 month after each treatment visit. A total of 24 follow-up calls will be made over the duration of the study. The purpose of the follow-up phone call is safety assessment and to document any adverse events. Calls will be made either by the clinical trial manager, the clinical research assistants, or the adverse event physician. Assessment will include the following:
 - Headache pain scale
- Long-term follow-up (Month 36, \pm 3 weeks): The purpose of the follow-up is to assess long-term safety and efficacy at the end of the study. The following exams will be conducted by the study subject's examining neurologist and study coordinator: (duration approximate 1 hour)
 - Vital signs
 - Physical exam
 - Neurological exam
 - Headache pain scale
 - EDSS
 - MSFC
 - 6 Minute Walk Test
 - 12 Item MS Walking Scale
 - MRI (brain, C and T spine) \pm Gadolinium enhancement will be scheduled to occur at end of study

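### No EDSS-Plus assessment is planned at Month 13, the primary time point, for a subject who stops before the 6th procedure

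*Protocol*

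**What the plan says.** Protocol 8.4 (withdrawal for adverse events) and 13.1 (discontinuation of individual subjects) carry the same sentence: "Subjects that are discontinued from the study will continue to undergo the follow-up visits relative to their last treatment". Section 13.1 continues: "All data gathered at these appointments will be included in the CRF and data set". Neither section says which visits are meant.

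The primary time point is fixed in Protocol 9.1.1: "The primary outcome will be the comparison of the composite scores at Month 13 (3 months after the 6th treatment/placebo) compared to baseline". Section 6.2 times the Month 13 visit in the same way: "The following exams will be conducted 3 months following the 6th treatment phase visit", with a window of one week either side. Year 1 procedures fall at Months 0, 2, 4, 6, 8 and 10.

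Protocol 6.3, the section on follow-up, contains two things. One is telephone safety contact: "Follow-up by phone will occur 48 hours, 1 week and 1 month after each treatment visit". The other is the Month 36 visit: "The purpose of the follow-up is to assess long-term safety and efficacy at the end of the study". Months 13 and 27 are called outcome assessments, not follow-up.

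SAP 4.1 limits the primary analysis to eligible subjects who finished the year of procedures and had the three-month assessment. SAP 3 leaves the missing-data method to be chosen once the data have been explored.

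**The concern.** The trial intends to keep seeing discontinued subjects and to keep their data, yet no section schedules the primary measurement at the primary time for those who stop before the 6th procedure. This is a gap in data collection. An analysis set can be revised before the analysis; an examination not done at Month 13 cannot be recovered.

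The triggers listed in 8.4 and 13.1 include acute worsening, a lasting unexplained neurological deficit and cognitive change. Most of these bear on disability, which is what EDSS-Plus measures, so the missing values are unlikely to resemble those of completers. Any Month 13 comparison of all randomised subjects would have to impute them by a method the SAP has not yet chosen.

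There is a second hazard. SAP 4.1 describes the primary reading by its distance from treatment and does not repeat the calendar month there. If the analysis set were widened, a reading taken three months after an early last procedure could be entered as the Month 13 value.

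**Working it through.** **1. The plan's own figures.** Inputs (Protocol 9.2, SAP 1.5): 20 per group, 40% against 5% responders, two-sided 0.05, pooled Z-test. Summing Bin(a; 20, 0.40) × Bin(b; 20, 0.05) over all outcomes (a, b) for which |a/20 − b/20| / √[p̄(1 − p̄)(2/20)] ≥ 1.96 gives 82.0%, in line with the stated power above 80%. (The normal approximation gives 77.7%.) Enrolment: 40 / (1 − 0.20) = 50. Expected losses: 0.20 × 50 = 10, or about 5 per arm. The number of subjects lost is therefore already budgeted for; what remains is bias.

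**2. If the outcome visit is re-timed.** Procedure k falls at Month 2(k − 1), so the visit falls at Month 2(k − 1) + 3. The Month 6 EDSS and MSFC are planned only for those still in the trial at that visit.

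| Last procedure | Month given | Re-timed visit | Months before 13 | Month 6 reading planned |
|---|---|---|---|---|
| 1 | 0 | 3 | 10 | no |
| 2 | 2 | 5 | 8 | no |
| 3 | 4 | 7 | 6 | no |
| 4 | 6 | 9 | 4 | yes |
| 5 | 8 | 11 | 2 | yes |
| 6 | 10 | 13 | 0 | yes |

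The first five rows lie outside the one-week window. The sixth does not.

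**3. If only section 6.3 applies.** The telephone calls carry no efficacy measure. The next EDSS-Plus after stopping is at Month 36, which is 36 − 13 = 23 months after the primary time point. Neither reading gives a Month 13 value for the first five rows.

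**4. How much the unmeasured subjects could matter.** This is an illustration. It takes the protocol's rates as observed in 20 completers per arm (8 and 1 responders), restores 5 unmeasured subjects per arm, and assumes that no treated leaver responds. The number of placebo leavers who respond is varied. Pearson χ² = N(ad − bc)² / (product of the four margins).

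| Treatment | Placebo | Fisher p | χ² | χ² p |
|---|---|---|---|---|
| 8/20 | 1/20 | 0.020 | 40 × 140² / (20 × 20 × 9 × 31) = 7.02 | 0.008 |
| 8/25 | 1/25 | 0.023 | 50 × 175² / (25 × 25 × 9 × 41) = 6.64 | 0.010 |
| 8/25 | 2/25 | 0.074 | 50 × 150² / (25 × 25 × 10 × 40) = 4.50 | 0.034 |
| 8/25 | 3/25 | 0.171 | 50 × 125² / (25 × 25 × 11 × 39) = 2.91 | 0.088 |

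One responding placebo leaver crosses 0.05 under Fisher's test; two are needed under chi-square. The plan allows either test.

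**5. Power if all 25 per arm are measured and analysed.** Treated rate = 0.8 × 0.40 + 0.2 × x, where x is the assumed response in treated leavers. The leavers' rates are assumptions, not figures from the documents.

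| Assumption for leavers | Rates | Exact pooled Z | Fisher |
|---|---|---|---|
| None respond, either arm | 32% v 4% | 81.0% | 67.1% |
| Treated respond at 5% | 33% v 5% | 78.3% | 64.6% |
| Half the effect kept (x = 22.5%) | 36.5% v 5% | 85.4% | 74.3% |
| Full effect kept | 40% v 5% | 90.7% | 82.2% |

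For comparison, 20 completers per arm at 40% against 5% give 82.0% and 71.6%.

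**The case against.** The strongest reply is that the text does not prove any re-timing of the outcome visit. Section 6.3 reserves the word follow-up for the calls and the Month 36 visit, and the calls are already timed from each procedure. That is correct. What the documents show is an undefined term and a missing rule. It does not rescue the plan, because the narrower reading leaves a longer gap.

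A reader might also infer that nobody who stops in year 1 is measured at Month 13. That is too broad: after the 6th procedure, at Month 10, the three-month visit still falls at Month 13. Nor is an early reading the only efficacy information. Subjects who reach Month 6 have EDSS and MSFC then, and the Month 36 visit repeats both; MSFC includes T25FW and 9HPT. None of these is a Month 13 value.

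The last reply is that extra data would change nothing, because the SAP's primary set excludes these subjects and the sample size already assumes 20 evaluable per arm. This stands against collecting the data alone. It is a reason to pair collection with an analysis that uses the values, not a reason to leave them uncollected.

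**Conclusion.** The gap is real in a limited form: for a subject who stops before the 6th procedure, neither document plans an EDSS-Plus at Month 13. Ten of 50 is a ceiling. The 20% attrition is not confined to that period: some subjects may leave later, before any procedure (enrolment is defined as consent), or decline to return. Likewise, a shift of 5/25 = 20 percentage points in one arm's rate would need all five losses in that arm to be early leavers with the same status.

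The case for informative loss rests on the listed triggers; the documents give no rates by reason. A reader might infer that the loss differs by arm, but nothing in the documents shows that. The illustration in the working shows sensitivity, not an expected result. The plan's stated power and enrolment are not in question.

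Sections 8.4 and 13.1 also contradict each other on replacement of discontinued subjects: the first says they are replaced, the second that they are not. These must be reconciled, since the answer determines who makes up the randomised set.

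**What to change.** In Protocol 8.4 and 13.1, define the follow-up visits and add wording such as: *Subjects who stop before the 6th procedure and have not withdrawn consent will be asked to attend at Month 13, counted from their first procedure, for EDSS, T25FW and 9HPT by the blinded examiner. A reading taken three months after an earlier last procedure will not be used as the Month 13 value.*

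In SAP 4.1, add an analysis of all randomised subjects at Month 13 that uses these values, and state in advance how those still missing are handled. Include subjects who never had a procedure, since they have no first-procedure date. Without this step the completer set would exclude the new data.

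Reconcile the two statements on replacement.

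The cost is protocol and SAP wording, plus about one extra clinic assessment for each of up to 10 subjects already under follow-up. It needs no new staff and no invasive procedure. Some leavers will decline, so the gap will narrow but not close.
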